5.4.3. Other critical structures

The following other critical structures will be contoured on the free-breathing CT image for both CFRT and SABR patients.

- 1) Spinal Cord: The spinal cord should be contoured on every axial CT slice as the bony limits of the spinal canal, extending from at least 10 cm superior to the superior-most extent of the PTV, and caudally 10 cm below the inferior-most extent of the PTV.
- 2) Heart: The heart, along with the pericardial sac, should be contoured from its base to apex, beginning superiorly at the level of the inferior aspect of the aortic arch (aorto-pulmonary window) and extending inferiorly to the apex of the heart.
- 3) Esophagus: The entire circumference of the esophagus including the outermost fatty adventitia should be contoured based on mediastinal windowing, and should be contoured on every axial CT slice at least 10 cm cranial and caudal to the PTV.
- 4) Brachial Plexus: The right and left brachial plexi should be contoured separately. The defined ipsilateral brachial plexus originates from the spinal nerves exiting the neuroforamina on the involved side from around C5 to T2. However, for the purposes of this protocol, only the major trunks of the brachial plexus will be contoured using the subclavian and axillary vessels as a surrogate for identifying the location of the brachial plexus. This neurovascular complex will be contoured starting proximally at the bifurcation of the brachiocephalic trunk into the jugular/subclavian veins (or carotid/subclavian arteries) and following along the route of the subclavian vein to the axillary vein ending after the neurovascular structures cross the second rib.
- 5) Proximal bronchial tree: Should extend from 2 cm above the carina and include the right and left main bronchi, extending distally to the first bifurcation of the named bronchi.
- 6) Trachea: Should include the tracheal and cartilage rings extending at least 10 cm superior to the superior extent of the PTV.
- 7) Great Vessels: Should include the aorta, right and left pulmonary arteries, and superior vena cava at least 10 cm superior and inferior to PTV.
- 8) Skin: The skin will be defined as a rind encompassing the outer 0.3 cm of the body surface.

CFRT

Tissue	Max Dose to 0.03 cc (Gy)	Other Constraints
Spinal cord	47 Gy	
Esophagus	70 Gy	Mean <34 Gy*
Brachial Plexus	66 Gy*	
Heart/Pericardium	70 Gy	60 Gy to <33%; 45 Gy to <66%
Great Vessels	70 Gy*	
Trachea	70 Gy	
Central Airways	68 Gy	

SABR

Tissue	3 fraction			5 fraction		
	Volume	Vol Max	Max to 0.03 cc	Volume	Vol Max	Max to 0.03 cc
Spinal cord	<0.35 cc	18 Gy	21.9 Gy	<0.35 cc	23 Gy	30 Gy
Esophagus	<5 cc	17.7 Gy*	25.2 Gy	<5 cc	19.5 Gy	35 Gy
Brachial Plexus	<3 cc	20.4 Gy*	24 Gy*	<3 cc	27 Gy*	30.5 Gy*

Heart/Pericardium	<15 cc	24 Gy*	30 Gy	<15 cc	32 Gy*	38 Gy
Great Vessels	<10 cc	39 Gy*	45 Gy	<10 cc	47 Gy*	53 Gy
Trachea	<4 cc	15 Gy*	30 Gy	<4 cc	16.5 Gy*	40 Gy
Central Airways	<0.5 cc	18.9 Gy*	23.1 Gy	<0.5 cc	21 Gy*	33 Gy
Skin	<10 cc	30 Gy*	33 Gy*	<10 cc	36.5 Gy*	39.5 Gy*

*Constraints marked by asterisk are guidelines and will not be scored as a protocol deviation if not achieved.

Other constraints represent absolute limits and treatment delivery that cannot meet these constraints will constitute a major protocol violation.

6. Pulmonary Function Test, 6-min Walk Test, and BODE Index

We will perform PFTs (including spirometry, lung volumes and diffusing capacity) at pre-treatment and at 6-month follow-up, 6-min walk test (recommended but optional at pre-treatment and follow-up), and calculate the BODE (body mass index, airflow obstruction, dyspnea, exercise capacity) index for those who complete the 6-min walk tests.

7. Adverse Event Reporting

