2.2. Secondary objectives

- 1) Assess long-term toxicity from 4D CT ventilation image-guided personalized radiotherapy as scored by the NCI-Common Terminology Criteria for Adverse Events (CTCAE) version 4.0.
- 2) Estimate the clinical significance of 4D CT ventilation image-guided personalized radiotherapy by evaluating: (1) clinical and subclinical endpoints for pulmonary toxicity (including symptomatic radiation pneumonitis and post-treatment changes in pulmonary function tests (PFTs), 6-min walk test, and BODE index); (2) correlation between those endpoints and functional dose-volume parameters.
- 3) Assess local tumor control after 4D CT ventilation image-guided personalized radiotherapy.
- 4) Quantify the dosimetric significance of 4D CT ventilation image-guided adaptive radiotherapy.

- 5) Investigate whether in vivo EPID dosimetry can detect clinically significant anatomic changes for patients treated with CFRT.

3. Patient Selection

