9.1. Study endpoints

Primary endpoints

(1) Grade ≥ 3 radiation pneumonitis, (2) grade ≥ 3 esophagitis, (3) other grade ≥ 3 AEs that occur ≤ 12 months after treatment and drop-out defined as definitely, probably, or possibly related to the protocol treatment.

Secondary endpoints

- 1) Long-term toxicity, as scored by the NCI-CTCAE version 4.0.
- 2) Clinical and subclinical endpoints for pulmonary toxicity (including radiation pneumonitis and post-treatment changes in PFTs, 6-min walk test, and BODE index).
- 3) Correlation between the clinical/subclinical endpoints for pulmonary toxicity and functional dose-volume parameters.

- 4) Local tumor control.
- 5) Lung functional dose-volume metrics, including the functional V_x (fV_x) (% volume receiving $\geq x$ Gy) and functional mean lung dose (fMLD).

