9.3. Analysis plan

Primary endpoints: (1) Grade ≥ 3 radiation pneumonitis, (2) grade ≥ 3 esophagitis, (3) other grade ≥ 3 AEs that occur ≤ 12 months after treatment and drop-out defined as definitely, probably, or possibly related to the protocol treatment.

We will estimate the rates of AEs and tolerability with exact 95% confidence intervals. 4D CT ventilation image-guided personalized radiotherapy will be considered safe if AE rates are lower than the following acceptable rates (determined based on the published toxicity data for locally advanced lung cancer patients): (1) grade ≥ 3 radiation pneumonitis, 13% (Jiang *et al.*, 2012), (2) grade ≥ 3 esophagitis, 21% (Wei *et al.*, 2006), and (3) other grade ≥ 3 AEs and drop-out, 20% (Bradley *et al.*, 2015).

Secondary endpoints

Analyses of secondary endpoints will be primarily descriptive rather than hypothesis testing.

Toxicity will be summarized by frequency and exact 95% confidence intervals, overall and separately by grade and organ system.

The clinical significance of 4D CT ventilation image-guided personalized radiotherapy will be estimated by evaluating: (1) clinical and subclinical endpoints for pulmonary toxicity (including radiation pneumonitis, PFTs, 6-min walk test, and BODE index); (2) correlation between those endpoints and functional dose-volume parameters. Radiation pneumonitis will be assessed at follow-up every 3 months for a minimum of 2 years after treatment using the NCI-CTCAE version 4.0. Post-treatment changes in PFTs (including spirometry, lung volumes and diffusing capacity), 6-min walk test, and the BODE index will be evaluated at the time of 6-month follow-up. Using composite treatment plans, the following lung functional dose-volume parameters will be calculated: functional mean lung dose (fMLD), functional V_{20} (fV_{20}) and functional effective dose (fD_{eff}) (Vinogradskiy *et al.*, 2013), which will be correlated with the endpoints for pulmonary toxicity.

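### With an optional walk test and BODE computed only for completers, patients too breathless to walk at 6 months have no result, so these two secondary measures probably understate worsening

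*Combined protocol and SAP*

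**What the plan says.** Section 6 describes the "6-min walk test (recommended but optional at pre-treatment and follow-up") and says that the study will "calculate the BODE (body mass index, airflow obstruction, dyspnea, exercise capacity) index for those who complete the 6-min walk tests". It does not define completion.

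Section 2.2, objective 2, lists "post-treatment changes in pulmonary function tests (PFTs), 6-min walk test, and BODE index" among the measures of pulmonary toxicity, and Section 9.1 repeats them as secondary endpoint 2. Section 9.3 says of PFTs, the walk test and BODE that they "will be evaluated at the time of 6-month follow-up", and then correlates the pulmonary-toxicity endpoints with fMLD, fV20 and fDeff. The same section states: "Analyses of secondary endpoints will be primarily descriptive rather than hypothesis testing".

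Appendix III schedules the walk test and BODE at baseline and, by footnote, once after treatment, at 6 months. It marks the contrast CT as recommended but carries no such mark for the walk test or BODE.

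The documents do not say how to score or report a patient who cannot walk, do not ask for the reason for a missed test, and plan no missing-data handling or sensitivity analysis for these measures.

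**The concern.** Whether a patient has a 6-month walk or BODE result can depend on the outcome being measured. Section 7.3 describes pneumonitis as arising weeks to months after treatment, with fatigue and shortness of breath among its features, and these limit walking. By Section 6's own description, dyspnea and exercise capacity are components of BODE. A patient who cannot walk because of breathlessness is thus among the most informative for this endpoint, yet has no value on it. With only one post-treatment test, a missed result is not recovered later.

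Two parts of objective 2 are at stake. The summary of change in walk distance and BODE would lean toward less worsening. The correlation with functional dose would tend to weaken, because the worst outcomes are cut from the range. If reasons are not recorded at the visit, inability to walk may be impossible to separate from refusal afterwards.

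**Working it through.** The plan gives no completion rate, expected change or precision for the walk test or BODE, so there is no figure of its own to reproduce. What follows checks whether the gap could matter in a cohort of this size.

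**Inputs from Section 9.4:** 34 patients; 37% dead by 12 months (a figure for locally advanced NSCLC); 1% unrelated drop-out; 13% grade ≥3 pneumonitis.

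**Assumed inputs:** constant hazard of death; about 20% of walkers worsen, by whatever threshold is chosen; *u* living patients cannot walk for respiratory reasons; all others have both tests.

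**Patients alive at 6 months.** Survival is √(1 − 0.37) = √0.63 = 0.794. With half of the 1% drop-out, 0.794 × 0.995 = 0.790, and 34 × 0.790 = 26.9, about 27. As a low bound, if the full 38% loss had already occurred, 34 × 0.62 = 21.

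**A plausible number of non-walkers.** 27 × 0.13 = 3.5. The plan's own grade ≥3 pneumonitis rate thus points to about 3 or 4 cases over 12 months, not all of them active at month 6. Five of 27 (18.5%) is above that rate and is shown as a high value.

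**Formulas.** With N alive, *w* is 0.20 × (N − *u*) rounded to a whole patient. Completers only: *w*/(N − *u*). Non-walkers counted as worsened: (*w* + *u*)/N. Intervals are exact 95% (Clopper-Pearson).

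| N | u | Completers only | Non-walkers counted | Difference (points) |
|---|---|---|---|---|
| 27 | 1 | 5/26 = 19.2% (6.6-39.4) | 6/27 = 22.2% (8.6-42.3) | 3.0 |
| 27 | 3 | 5/24 = 20.8% (7.1-42.2) | 8/27 = 29.6% (13.8-50.2) | 8.8 |
| 27 | 4 | 5/23 = 21.7% (7.5-43.7) | 9/27 = 33.3% (16.5-54.0) | 11.6 |
| 27 | 5 | 4/22 = 18.2% (5.2-40.3) | 9/27 = 33.3% (16.5-54.0) | 15.2 |
| 27 | 6 | 4/21 = 19.0% (5.4-41.9) | 10/27 = 37.0% (19.4-57.6) | 18.0 |
| 21 | 3 | 4/18 = 22.2% (6.4-47.6) | 7/21 = 33.3% (14.6-57.0) | 11.1 |

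The completer-only figure stays near 20% however many patients cannot walk, so nothing in that summary would reveal the problem.

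**Optional uptake.** If 60% of those able to walk take the test (assumed), 27 × 0.6 = 16 patients have a 6-month result when all can walk, and 27 × 0.8 × 0.6 = 13 when 20% cannot. Voluntary skipping therefore costs precision on top of any bias. A skipped baseline test also removes the patient, since change needs both tests.

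**The case against.** The strongest reply is about scope. The walk test and BODE are two of four measures in a secondary, descriptive set. The other two are CTCAE pneumonitis, graded every 3 months for at least 2 years, and 6-month PFTs, which are not labelled optional. A patient too breathless to walk is still due CTCAE grading. This stands. A reader might infer that the trial's safety conclusion, or its whole assessment of pulmonary toxicity, is biased. The documents do not support that: the primary endpoints in Section 9.1 do not use the walk test. But the other measures do not repair the walk and BODE results, which are reported and correlated in their own right.

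Second, BODE needs an exercise value, so Section 6 can be read as a condition of calculation rather than a decision to exclude breathless patients. That is fair, and completion is undefined, so a patient who stops early may or may not count. The effect is the same while no rule says what to do.

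Third, the direction of bias is inferred. Patients may skip an optional test by choice or for logistics, including fit ones. The Section 7.3 statement that about 80% of pneumonitis is manifest within 10 months concerns onset; it does not show that toxicity is active at the 6-month visit. This also stands, and is why the bias is called likely and not certain.

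Fourth, the 37% mortality is for locally advanced NSCLC, while the trial also takes SABR patients with early-stage or limited metastatic disease. The survivor count may be higher than 27.

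**Conclusion.** The point holds for the walk-test and BODE components of secondary objective 2. Section 6, read with the silence of Section 9.3, leaves patients who cannot walk for respiratory reasons without a result. This probably understates worsening and weakens the correlation with fMLD, fV20 and fDeff.

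The documents cannot fix the size. On the assumptions above, 3 to 5 non-walkers among 27 survivors shift the proportion worsened by about 9 to 15 percentage points, and 1 to 6 shift it by about 3 to 18. These are illustrations, not forecasts. A reader might want to state the bias in metres, but the documents give no walk distances from which to do so. Nor do they show that the test has to be compulsory: that trades patient and staff burden against completeness, and it would not by itself give a result for someone unable to walk.

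A change is worth making because the reason for a missed test has to be captured when it happens.

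**What to change.** In Sections 6 and 9.3, keeping the test optional if the sponsor wishes:

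1. Define completion so that a test stopped early counts, with the distance walked.
2. Record on the CRF the reason for every missed or stopped test: respiratory, other medical, refusal or logistics, death.
3. Among patients with a baseline test, give a living patient who cannot walk at 6 months for a respiratory reason the lowest rank on walk change and the worst BODE exercise category. State the BODE scoring table, which the documents do not give. Use a rank-based summary and correlation, and show the completer-only result beside it.
4. Report separately the numbers unable to walk for respiratory reasons, dead, and missing for other reasons, and the number with no baseline test, whom step 3 cannot recover.
5. Reconcile Appendix III with Section 6 on whether the walk test and BODE are optional.

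The cost is one CRF field, some protocol wording and a little more analysis. Worst-rank scoring changes what is being estimated, which is why both results should be shown, and the reported changes may look less favourable.

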7.1. Adverse event monitoring

Subjects will be carefully monitored for adverse events. This monitoring includes clinical and laboratory tests. This study will utilize the NCI-CTCAE version 4.0 for toxicity and Adverse Event Reporting. A copy of the NCI-CTCAE version 4.0 can also be downloaded from <http://ctep.cancer.gov/reporting/ctc.html>. Adverse events will be assessed each cycle, and the highest grade according to NCI-CTCAE version 4.0 will be recorded. Adverse events will be assessed in terms of seriousness, severity, and relationship to the study procedures.

7.2. Adverse Event Definitions

Adverse Events (AEs)

Any unfavorable and unintended sign (including an abnormal laboratory finding), symptom, or disease temporally associated with the use of a medical treatment or procedure regardless of whether it is considered related to the medical treatment or procedure (attribution of unrelated, unlikely, possible, probable, or definite).

Serious Adverse Events (SAEs)

Any adverse experience occurring during any part of the protocol treatment and 30 days after that results in any of the following outcomes:

- Results in death.
- Is life-threatening (refers to an AE in which the patient was at risk of death at the time of the event. It does not refer to an event which hypothetically might have caused death if it were more severe).
- Requires inpatient hospitalization or prolongation of an existing hospitalization
- Results in persistent or significant disability or incapacity. (Disability is defined as a substantial disruption of a person's ability to conduct normal life functions).
- Is a congenital anomaly/birth defect.
- Is a medically important event. This refers to an AE that may not result in death, be immediately life threatening, or require hospitalization, but may be considered serious when, based on appropriate medical judgment, may jeopardize the patient, require medical or surgical intervention to prevent one of the outcomes listed above, or involves suspected transmission via a medicinal product of an infectious agent.

Intensity (Severity) of the Adverse Event

The intensity or severity of AEs will be graded according to the NCI-CTCAE version 4.0 criteria.

Adverse Event Documentation

All AEs occurring after the subject has received the first dose of investigational treatment will be fully recorded in the subject's case record form. Documentation will be supported by an entry in the subject's file. Each event will be described in detail along with start and stop dates, severity, relationship to study treatment, action taken and outcome.

7.3. Study Procedure Adverse Events

Treatment-related AEs will be categorized and graded based on the NCI-CTCAE version 4.0. Treatment should be interrupted for Grade 4 in-field toxicity and resumed when that toxicity has decreased to Grade ≤ 2 as detailed below. If treatment is interrupted for >2 weeks, the patient should be removed from study treatment. Expected AEs include reversible or permanent alopecia, bone marrow toxicity, skin pigmentation, esophagitis and radiation pneumonitis. Radiation-induced myocarditis or transverse myelitis rarely occurs at doses <50 Gy. Radiographic evidence of density change and subsequent fibrosis of the lung will occur within lung volume receiving ≥ 20 Gy, usually within the first six months after initiation of treatment.

Esophagitis

Esophageal complaints are common with thoracic radiotherapy. Esophagitis typically manifests as dysphagia, odynophagia, and reflux symptoms. Acute esophagitis occurs during a course of treatment and often persists for several weeks after treatment (Werner-Wasik *et al.*, 2010). The symptoms of severe esophagitis (Grade ≥ 3) typically peak 4-8 weeks from the beginning of treatment. Late esophageal damage, typically stricture and associated dysphagia, develops ~ 3 -8 months after treatment. Esophagitis does not constitute a reason to interrupt or delay radiotherapy provided oral intake is sufficient to maintain hydration. If Grade 3 or 4 esophagitis occurs, and a treatment interruption is being considered, every effort should be made to limit it to 3 treatment days or less.

Acute esophageal toxicity should be pharmacologically managed with the following approach and should be initiated at the first signs or symptoms of esophageal toxicity. Recommended treatments are as follows:

- 1) Patients should be advised to avoid alcoholic, acidic, or spicy foods or beverages.
- 2) Ketoconazole 200 mg PO q day OR Fluconazole 100 mg PO q day until completion of radiation.
- 3) Mixture of: 2% viscous lidocaine: 60 cc, Mylanta: 30 cc, sucralfate (1 gm/cc): 10 cc; Take 15-30 cc PO q3-4 hrs prn (Contraindications: pts on Dilantin, Cipro, Digoxin).
- 4) Ranitidine 150 mg PO BID (or other H₂ blocker or a proton pump inhibitor such as omeprazole) until the completion of radiation.
- 5) Grade 4 esophagitis: hold radiotherapy until Grade ≤ 2 .
- 6) Occasionally, narcotics may be required.

Radiation pneumonitis

Radiation pneumonitis is a subacute (weeks to months from treatment) inflammation of the end bronchioles and alveoli. Approximately 80% of radiation pneumonitis is clinically manifest within 10 months of treatment (Marks *et al.*, 2010). The clinical picture may be very similar to acute bacterial pneumonia, with fatigue, fever, shortness of breath, nonproductive cough, and a pulmonary infiltrate on chest x-ray. The infiltrate on chest x-ray should include the area treated to high dose, but may extend outside of these regions. The infiltrates may be characteristically "geometric" corresponding to the radiation portal, but may also be ill defined.

Patients reporting symptoms as above will be promptly evaluated and treated. Mild radiation pneumonitis may be treated with nonsteroidal anti-inflammatory agents or steroid inhalers. More significant pneumonitis will be treated with systemic steroids,

bronchodilators, and pulmonary toilet. Supra- and concurrent infections should be treated with antibiotics. Consideration of prophylaxis of opportunistic infections should be considered in immunocompromised patients.

It is unlikely that symptomatic pneumonitis will occur during the weeks radiation is actually delivered to the patients. However, if a patient experiences pneumonitis before completing therapy, therapy will be put on hold until symptoms resolve. At that point, a clinical decision whether to finish therapy will be made by the treating physicians.

AEs may be spontaneously reported by the patient and/or in response to an open question from study personnel or revealed by observation, physical examination, or other diagnostic procedures must be reported to Co-PI, [name] (or designee).

Reporting Forms:

- SAE Report Form
- Reporting to the FDA: US FDA MedWatch 3500A
(<http://www.fda.gov/Safety/MedWatch/HowToReport/DownloadForms/default.htm>)

Each serious AE will be followed up until resolution or stabilization, by submission of updated reports to the Co-PI, [name]. Both serious and non-serious AEs will be reported in accordance with UCD Institutional Review Board (IRB) Administration and UCD Cancer Center policies. The UC Davis IRB can be reached at [contact].

8. Data Review and Management

8.1. Patient Registration

Once signed, informed consent has been obtained and all pre-treatment evaluations have been performed, patients will be entered on study according to UCD Cancer Center policy. To register a patient, the research nurse or data manager will complete the Eligibility Checklist and the Patient Registration Form. A patient accession number will then be assigned. Study biopsy and administration of study drug may not be initiated until the patient is registered. An original signed and dated participant Informed Consent document will reside in a secured location within the UCD Department of Radiation Oncology. Copies of the signed and dated Informed Consent document will be provided to the study participant and UCD Health System Information Management for inclusion in the participant's UCD Health System Medical Record.

